6.1 Study treatment

As per the USM follow-up notification dated 06-Dec-2022, the study treatment has been permanently discontinued; the last dose administered was 08-Aug-2022.

The investigational treatment for this study is branaplam and matching placebo. Novartis will supply branaplam and matching placebo in 6 mL vials containing 5 mL of study treatment. The vials will be packed in boxes containing 4 vials each. All eligible participants will be randomized via Interactive Response Technology (IRT) to one of the available treatment arms.

Details on the requirements for storage and management of study treatment, and instructions to be followed for preparation /dispensing, and administration of study treatment are outlined in the Instructions for Use.

6.1.1 Investigational and control drugs

Table 6-1 Investigational and control drug

Investigational/ Control Drug (Name and Strength)	Pharmaceutical Dosage Form	Route of Administration	Supply Type	Sponsor (global or local)
LMI070 (branaplam) 17.5 mg/5 mL	Oral solution	Oral use	Double blind; vials	Sponsor (global)

Investigational/ Control Drug (Name and Strength)	Pharmaceutical Dosage Form	Route of Administration	Supply Type	Sponsor (global or local)
matching placebo 5 mL	Oral solution	Oral use	Double blind; vials	Sponsor (global)

6.1.2 Treatment arms/group

At the Week 1 visit, participants will be randomized to one of the following treatment arms in a ratio of 4:1, active vs. PBO

- Cohort 1: Treatment Arm A: Branaplam 56 mg oral solution or matching PBO, once weekly
- Cohort 2: Treatment Arm B: Branaplam 112 mg oral solution or matching PBO, once weekly
- Cohort 3:
 - Treatment Arm C: Branaplam 154 mg oral solution or matching PBO, once weekly or
 - Treatment Arm X: Branaplam 84 mg oral solution or matching PBO, once weekly or
 - Treatment Arm Y: Branaplam 28 mg oral solution or matching PBO, once weekly

Treatment Arm assignment for an individual participant will be determined by which treatment arms are open at the time of the participant screening.

For Treatment Arms C, X and Y, only one of the three will be initiated in Cohort 3. PBO is embedded within each Treatment Arm.

6.1.3 Treatment duration

All participants who are randomized will enter the Core Treatment Period, receiving the investigational treatment or PBO for at least 16-weeks in the DRF portion. After the DRF period, all participants will continue on their assigned study treatment in the BE for up to approximately 53 weeks in total. The participants who are randomized earlier will have longer treatment durations. This will be impacted by the recruitment rate as well as the time necessary to complete the IA to confirm the OLE dose(s) account for the estimated variable time range for the BE. The Core Period duration (Dose Range Finding + Blinded Extension) may be extended beyond the estimated 53 weeks if recruitment is slower than planned.

Once the last randomized participant within all open Cohorts completes the DRF period, the data for the IA will be compiled while this last randomized participant continues to the BE. This timing will be closely monitored to assess the appropriate timing of the End of the Blinded Extension, and all sites will be notified in the preceding months so they can plan accordingly. All assessments for the End of Core visit will be completed as specified in [Table 8-2](#), [Table 8-3](#) and [Table 8-4](#).

Treatment duration for OLE is for approximately 52 weeks, after which a subsequent extension study will be available for participants to roll into if this protocol was not previously amended to extend the OLE.

Participants may be discontinued from treatment with the study drug at any time due to unacceptable toxicity, disease progression and/or at the discretion of the investigator or the participant.

6.2 Other treatment(s)

No additional treatment beyond investigational drug is provided in this trial. An overview of the prohibited medication is given in [Table 6-2](#).

6.2.1 Concomitant therapy

As per the USM, study treatment has been permanently discontinued after approximately 4 months of temporary suspension; thus, there are no longer restrictions for concomitant drugs. Investigators should follow medical judgment and standard of care when prescribing new medications.

All medications administered must be recorded on the Prior and Concomitant Medications electronic case report form (eCRF). All medications, procedures, and significant non-drug therapies (including physical therapy and blood transfusions) administered within 6 months prior to the Screening visit, and after the participant was enrolled into the study, must be recorded on the Prior and Concomitant Medications eCRF. Any medications, procedures, and significant non-drug therapies taken by the participant within the timeframe defined in the entry criteria prior to the start of the study should also be recorded.

Each concomitant drug must be individually assessed against all exclusion criteria and prohibited medication. If in doubt, the Investigator should contact the Novartis medical monitor before randomizing a participant or allowing a new medication to be started. If the participant is already randomized and/or has received treatment with study drug, contact Novartis to determine if the participant should continue participation in the study.

Pre-USM : In addition, participants should be on a stable dose and regimen of permitted chronic concomitant medications for at least 6 weeks prior to receiving the first dose of study drug which in the medical judgement of the Investigator is not anticipated to change during the study. If new medications are initiated during Screening, laboratory evaluations must meet eligibility criteria before first dose of study drug.

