6.2.1.1 Permitted concomitant therapy requiring caution and/or action

THC /Cannabinoid containing substances are neither categorized as CYP3A4/5 substrates with narrow therapeutic index or as a sensitive CYP3A4/5 substrate nor as strong or moderate CYP3A4 inhibitors by e.g. FDA (see [Table 6-2](#)). However, interaction as substrate and/or inhibitor of CYP3A4 cannot completely be excluded. Therefore, the use of THC /Cannabinoid containing substances is allowed as per local regulations and/or local medical practice with caution if in the opinion of the Investigator, use does not represent an exclusionary condition, does not constitute abuse and does not affect cognition, and provided that participants are currently treated with a stable regimen for at least 12 weeks prior to first dose of study drug. If initiated during the study, use must be withheld for 72 hours prior to any cognitive and/or motor assessments.

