6.2.2 Prohibited medication

As per the USM follow-up notification dated 06-Dec-2022, the study treatment has been permanently discontinued, therefore the prohibited medications referenced below in Table 6-2 are no longer applicable.

In vitro experiments showed that branaplam can be metabolized via Human Cytochrome P450 3A4 (CYP3A4) and direct glucuronidation. Therefore, there is a potential for inhibitors or inducers of CYP3A4 to alter the clearance of branaplam *in vivo* if oxidative metabolism is the major clearance pathway of branaplam. Branaplam should not be administered together with strong systemic inhibitors of CYP3A4 or with strong systemic inducers such as examples provided in the table below. Use of weak to moderate inhibitors of CYP3A4 should be avoided unless absolutely necessary.

Considering the direct glucuronidation pathway, there is a potential for inhibitors or inducers of UGT1A4, UGT1A7, and UGT1A9 to alter the clearance of branaplam *in vivo* if direct glucuronidation is the major clearance pathway of branaplam. However, no clinical relevant pan-UGT inhibitor is described in the literature and clinical relevant inhibition of all three identified UGTs is considered to be unlikely. Similar is true for the induction of UGTs. Therefore, potential UGT inhibitors/inducers are not prohibited and can be used with caution.

In vitro, results indicated that branaplam has a potential perpetrator risk on MATE2-K and OCT1 transporters, which might alter the disposition of MATE2-K and OCT1 substrates. Therefore, co-administration should be considered with caution and be avoided if possible as described in [Table 6-2](#).

Branaplam is considered to have a minor-to-moderate potential to inhibit CYP3A4/5 in a time-dependent manner impacting co-medications metabolized via CYP3A4/5 with a narrow therapeutic index. Due to the time-dependent inhibition, the decrease in enzyme activity may be amplified by administration of multiple doses. Therefore, use of known sensitive CYP3A4/5 substrates should be considered with caution and be avoided if possible ([Table 6-2](#)).

Use of the treatments displayed in the [Table 6-2](#) are not allowed after screening and at the time points specified.

Table 6-2 Prohibited Medications

Medications	Prohibition period	Action taken

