Medication(s) with “Potential risk of TdP” per qtldrugs list (Woolsley RL) These drugs include but are not limited to the following: aripiprazole, clozapine, deutetrabenazine, tetrabenazine, tiapride, levetiracetam, venlafaxine For a complete list and additional information, please visit CredibleMeds.org (website) and discuss with Sponsor	Within 14 days prior to first study dose administration or during the study	Discontinue the prohibited medication and substitute with an alternative medication without or with conditional risk of TdP (see recommendation for conditional TdP drugs below). After a patient has received study drug and if required due to life-threatening conditions or other exceptional circumstances indicating a high medical need for the use of these drugs the Investigator should use medical judgment carefully assessing the benefit risk for an individual patient under consideration. However, ECG monitoring will be required before starting these drugs and repeated once again when steady state (5 half-lives) of this drug is achieved. In case of any abnormality on a single ECG (>480 QTc) triplicate ECGs should be performed and mean values should be used for confirmation (mean QTc > 480 ms).

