### 2.6.2.1 Clinical endpoints

#### Summary tables

- The clinical endpoints will be summarized with appropriate descriptive tables by visit, and treatment group.

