#### 2.7.4.5 Neuropathy questionnaire

For neuropathy symptoms: worsening is defined for participants with a change in answer from “No” at baseline to “Yes” at post BL.

Flags by visit and by parameter level:

- By visit flag 1: adverse change indicated by a “YES” response to the same question in the questionnaire in at least 2 consecutive visits. flag the last visit with finding
- By visit flag 2: adverse change indicated by a “YES” response to a question in the questionnaire at any post baseline visit
- By visit flag 3 (recovery): Flag visits after **last** visit with finding (this finding stands for any worsening and don’t have to be consecutive) that the answer is back to baseline

Flags by participant level based on the above visit-based:

- Participant level flag 1: Participant without any finding at 2 consecutive visits
- Participant level flag 2: participants with any finding at 2 consecutive visits

- Participant level flag 3 (recovery): participants with any finding at 2 consecutive visits and followed by recovery (finding no longer present in all worsened questionnaire)
- Participant level flag 4 (partial recovery): participants with any finding at 2 consecutive visits and followed by partial recovery (finding no longer present in at least one of the worsened questionnaire)
- Participant level flag 4: Participant without any finding at any visit
- Participant level flag 5: participants with any finding at any visit
- Participant level flag 6 (recovery): participants with any finding and followed by recovery (finding no longer present in all worsened questionnaire)

Participant level flag 6.5 (partial recovery): participants with any finding and followed by partial recovery (finding no longer present in at least one of the worsened questionnaire) Note that, flags will be created based on weekly basis window instead of protocol scheduled visit window.

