#### 2.7.4.7 Overall safety findings and recovery

Results from Neuro findings including: NCS, neuro exam, symptoms (AEs and neuro questionnaire) will be summarized in one table for participants on active to show number (%) of participants with finding together with the information about recovery (yes/no) at the end of observation.

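### SAP 2.7.4.5 and 2.7.4.7 count a neuropathy symptom as recovered once it is absent, without showing whether the participant was taking a symptomatic drug

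*Protocol*

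**What the plan says.** **Drug rules.** Protocol 6.2.1 says of the period after permanent discontinuation: "thus, there are no longer restrictions for concomitant drugs. Investigators should follow medical judgment and standard of care when prescribing new medications". Section 6.2.2 adds: "therefore the prohibited medications referenced below in Table 6-2 are no longer applicable". Table 6-2 had barred, among others, "aripiprazole, clozapine, deutetrabenazine, tetrabenazine, tiapride, levetiracetam, venlafaxine", which it lists for torsade risk. Before discontinuation, section 6.6.2 left the treatment of adverse events to the investigator and required the medication to be recorded.

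**Symptom recovery.** In SAP 2.7.4.5 the participant-level flag for any finding reads "participants with any finding and followed by recovery (finding no longer present in all worsened questionnaire"); the flag for findings at two consecutive visits uses the same test. SAP 2.7.4.7 puts nerve conduction, neurological examination and symptoms (adverse events and questionnaire) in one table for the active arm, "together with the information about recovery (yes/no) at the end of observation". Neither section refers to medication.

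**UHDRS.** SAP 2.6.2.1 says: "The clinical endpoints will be summarized with appropriate descriptive tables by visit, and treatment group".

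**Medication data.** SAP 2.1.1 treats everything taken between first dose and end of study as one class of concomitant medication. SAP 2.4.2 tabulates it by ATC class and preferred term, unlinked to any outcome. Protocol Table 8-5 keeps recording medications at Weeks 33, 53 and 69.

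**The concern.** The Amendment 02 rationale gives two reasons for following branaplam participants for about a year after treatment stopped: to keep assessing signs and symptoms of peripheral neuropathy, and to collect more MRI data. Whether symptoms resolved is therefore a result that readers will look for. A symptom that goes away without treatment and one that is absent while a drug suppresses it support different conclusions about reversibility. The planned tables cannot tell them apart.

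UHDRS has a related but smaller problem. Drugs that could affect motor ratings became freely available partway through follow-up, and the by-visit tables do not show who was taking them. By Week 69 no placebo participants are scheduled, so no concurrent group shows background drug changes.

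**Working it through.** The plan states no figure on this point, so there is none to reproduce. The check covers which results are exposed, whether any existing SAP device deals with it, and how much one case matters.

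**1. Date of the lift.** From 05-Aug-2022 (suspension) to 06-Dec-2022 (permanent discontinuation) is 123 days, and 123 / 30.4375 = 4.04 months. This matches the roughly four months of suspension cited in protocol 6.2.1, so the lift dates from 06-Dec-2022.

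**2. Visits affected.** The last dose in the trial was 08-Aug-2022, so no Day 1 is later. The SAP's first version is dated 30-Nov-2021 and is described as preceding first patient first visit, so no Day 1 is earlier.
- Week 17 (Day 113): latest target is 08-Aug-2022 + 112 days = 28-Nov-2022. Every target precedes the lift. The SAP's UHDRS window runs to Day 169, which could reach 23-Jan-2023.
- Week 33 (Day 225): 06-Dec-2022 − 224 days = 26-Apr-2022. A first dose before that date puts the Week 33 target before the lift; otherwise it falls on or after it. Week 33 mixes both regimes.
- Week 69 (Day 477): 06-Dec-2022 − 476 days = 17-Aug-2021, which is before the trial started. Every Week 69 visit follows the lift; the earliest target is 30-Nov-2021 + 476 days = 21-Mar-2023.

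Table 8-5 schedules UHDRS only at Weeks 33 and 69. Placebo participants may leave at Week 33.

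**3. Existing devices in the SAP.**
- The on/off flag (2.1.1) concerns study drug only. Off-treatment status starts by 08-Aug-2022 + 14 days = 22-Aug-2022 at the latest, over three months before the lift.
- The medication table (2.4.2) is not linked to outcomes.
- A split at 06-Dec-2022 would not help the symptom rows: drugs for adverse events were allowed before then, and medication use differs between participants after it.

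**4. Rows exposed.** The questionnaire and adverse-event symptom rows are exposed. SAP 2.7.4.4 (motor, reflexes, sensory), 2.7.4.6 (nerve conduction) and 2.11.1 (NfL) each have their own recovery criterion.

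**5. Size.** Cohort 1 was planned at about 25, so at 4:1 about 25 × 4/5 = 20 received branaplam. The amendment rationale reports that almost half of the active arm had symptoms; I assume 9 or 10. One drug-suppressed case counted as recovery adds 1/10 = 10 to 1/9 = 11 percentage points. One to three cases add 10 to 33 points (1/10 to 3/9). For UHDRS, *m* new users with an effect of *d* points each would shift an active mean of 20 by *m* × *d* / 20. The documents give neither *m* nor *d*, so I put no figure on it.

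**6. Protocol text to reconcile.** Alongside the sentence lifting restrictions, section 6.2.1 still says, without a pre-discontinuation label: "Each concomitant drug must be individually assessed against all exclusion criteria and prohibited medication". Section 6.2.1.1 keeps, for cannabinoids: "If initiated during the study, use must be withheld for 72 hours prior to any cognitive and/or motor assessments". These passages and section 6.2.2 must be reconciled.

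**The case against.** Much of the opposing case stands, and it limits the point.

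- **Suppression is not shown.** The documents report no new drug start and no drug effect on a symptom or motor score. A reader might infer that suppressed symptoms have been reported as recovery; nothing supports that.
- **The lift is not the sole cause.** Table 6-2 has no category for neuropathic-symptom drugs, and adverse events could be treated throughout. Its conditional-risk list, which includes olanzapine, quetiapine and risperidone, allowed stable use, and even new starts with ECG monitoring. Some antipsychotic use could predate the lift.
- **No intercurrent-event rule was dropped for UHDRS.** A reader might set SAP 2.6.3 (not applicable) against the primary estimand, which handled prohibited drugs. That estimand concerned CSF mHTT at Week 17 and prohibited drugs taken without stopping study drug. Protocol 2.2 defines no secondary estimands.
- **Recovery is not judged on symptoms alone.** Examination, nerve conduction and NfL carry their own flags, and the questionnaire rule claims only that the finding is absent.
- **Deleting visits can bias.** Drugs tend to be started in patients who worsen. Removing their UHDRS assessments can make the remaining mean look better.
- **The stakes are limited.** All analyses are descriptive, the report is abbreviated and development has ended.

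None of this supplies the missing link between medication and symptom recovery. The limited stakes argue for a cheap fix, not for leaving the symptom rows uninterpretable.

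**Conclusion.** The concern holds for the symptom rows. SAP 2.7.4.5 and the questionnaire and adverse-event rows of 2.7.4.7 can count a drug-suppressed symptom as recovered, and nothing else in the SAP would reveal it. Under the assumption of about 10 symptomatic participants among about 20 on branaplam, each case is worth about 10 percentage points; the number of cases is unknown and may be zero.

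For UHDRS the documents support a question of presentation only: Week 33 mixes two drug regimes, and Week 69 follows the lift with no placebo participants scheduled. They do not support a stated bias in TMS, nor a conclusion that overall neurological recovery is overstated.

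This is a worthwhile improvement to a descriptive safety report. It does not affect any inferential result or dose decision.

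**What to change.** 1. In SAP 2.1.1, derive a flag from the Prior and Concomitant Medications eCRF for a neuropathic-symptom drug started or dose-increased after Day 1 and ongoing at the recovery assessment.
2. In SAP 2.7.4.5 and the symptom rows of 2.7.4.7, report three categories: *symptom absent, no symptomatic drug*; *symptom absent while on symptomatic drug*; *not recovered*. Show the first two separately. Do not reclassify the second as non-recovery, because true recovery and use for another reason are both possible.
3. In SAP 2.6.2.1, keep all UHDRS visits in the main table. Show by visit the number of participants with a newly started or changed anti-chorea or antipsychotic drug, and mark those assessments. Do not delete them.
4. Reconcile protocol sections 6.2.1, 6.2.1.1 and 6.2.2 on which drug rules applied after 06-Dec-2022.

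**Cost.** SAP wording, a medical review to assign drug classes, the derived medication flags and a few split rows. No new data are needed. The step resembles ones the SAP already takes, such as repeating volumetric MRI without participants who had subdural hematoma. The downside is small cell counts.

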6.2.1.1 Permitted concomitant therapy requiring caution and/or action

THC /Cannabinoid containing substances are neither categorized as CYP3A4/5 substrates with narrow therapeutic index or as a sensitive CYP3A4/5 substrate nor as strong or moderate CYP3A4 inhibitors by e.g. FDA (see [Table 6-2](#)). However, interaction as substrate and/or inhibitor of CYP3A4 cannot completely be excluded. Therefore, the use of THC /Cannabinoid containing substances is allowed as per local regulations and/or local medical practice with caution if in the opinion of the Investigator, use does not represent an exclusionary condition, does not constitute abuse and does not affect cognition, and provided that participants are currently treated with a stable regimen for at least 12 weeks prior to first dose of study drug. If initiated during the study, use must be withheld for 72 hours prior to any cognitive and/or motor assessments.

6.2.1.2 Concomitant SARS-CoV-2 / COVID-19 vaccines

SARS-CoV-2 / COVID-19 vaccines are not prohibited and there is no requirement for specific timing of receiving a vaccine prior to or after branaplam. Any instructions provided in the package inserts for each vaccine should be followed.

- Mechanistic studies have shown that branaplam acts as a glue between specific, un-spliced pre-mRNA sequences and the spliceosome. Currently available COVID mRNA vaccines consist of processed, mature mRNA which are not expected to be a substrate for branaplam.
- Currently available non-replicating viral vector SARS-CoV-2 vaccines require further cellular processing of resulting mRNA to produce the Spike protein. The distinct sequence of the Spike mRNA and the known MoA of branaplam make it unlikely that branaplam would interfere with processing of Spike mRNA.
- Based on the MoA of SARS-CoV-2 DNA based / Naked plasmid DNA and Inactivated SARS-CoV-2, vaccines are not expected to interact with branaplam.

Live attenuated SARS-CoV-2 vaccines are not contraindicated unless patient is immunocompromised.

